5.5.1. Primary outcome

The primary outcome of interest is conversion to psychotic disorder by 24 month follow up (definition in 5.4).

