7.2. Sample Size and Power

The size of the CHR sample is primarily determined by the aim of developing a prediction model for conversion to psychosis by 24 months (the primary outcome of interest). This will be achieved by combining data from the PRESCIENT and ProNET networks (i.e., the AMP SCZ dataset as whole), given that the protocols and schedule of assessments have been harmonised across the two networks. The projected CHR sample size for PRESCIENT is 937 and for ProNET 1,040 (combined n of 1,977). There is no uniform method for determining an adequate sample size for developing a prediction model⁹². In this sample size calculation, the method recently described by Riley et al⁹³ was used. Minimum sample size calculations required for various scenarios are provided in table 1. below. Specifically, the sample sizes were derived for the scenarios of having low, medium or high prediction performance and also for the number of parameters in the model being 10, 20, 30, 40 or 50. Conversion to psychosis is a time-to-event outcome and therefore a survival model such as Cox regression is appropriate. The table below shows the sample sizes for the survival outcome, assuming a conversion rate of 15% over 2 years (number of events=300).

Table 1. Minimum sample sizes for survival outcome.

		Number of parameters in model				
		10	20	30	40	50
Predictive performance	low	422	843	1265	1686	2108
	medium	398	796	1193	1591	1989
	high	366	732	1098	1464	1830

It is undesirable to have the number of parameters above 30 as this would result in a prediction model that is overly cumbersome in real-world settings. As indicated in the table, the minimum sample size for a model with 30 parameters is estimated to be between 1100 and 1300. However, as in all medical research, larger sample sizes lead to more robust models and it would therefore be desirable to achieve a sample size larger than this minimum recommendation. Therefore, we aim to assemble as large a sample as possible given the constraints of the length of the recruitment period and the number of recruitment sites. The sample size calculations presented in the table indicate that the overall AMP SCZ sample size of 1,977 is adequate for developing a prediction model with ~30 parameters that has high predictive performance, while still allowing a subset of the data to be 'held back' for external validation purposes (see section 14).

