7.3. Recruitment

Research Assistants (RAs) within their respective clinical service will recruit help-seeking clients who are being cared for and supported within clinical services. The RAs will identify young people who potentially meet eligibility criteria via reviewing medical records of new referrals, consulting with clinicians working in the recruiting clinics and/or sitting in on clinical review at the respective recruitment sites or other site-appropriate study recruitment activities. This method closely aligns with other studies recruiting this clinical population. Initial suitability will be established by the fact that the young person appears to meet CHR criteria, falls within the targeted age range, appears competent to consent to the study, and there is no obvious indication that he/she meets exclusion criteria. Healthy control participants will be recruited from the community using a variety of methods, including social media posts and word of mouth as well as from an existing list of HC participants in previous studies who have indicated they would like to participate in future research projects.

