TREATMENT AND HEALTH SERVICE UTILISATION	Psychosocial/ pharmacological treatment/service use		✓C	✓	✓C	✓			✓						✓C	✓	✓C	

Notes:

1. The Baseline visit needs to be conducted within 3 weeks of the screening visit. If not, the screening visit will need to be repeated. The study team will endeavour to schedule all other visits up to month 12 within +/- 1 week of their due date. For example, a Month 6 visit can occur up to 1 week prior to or after its due date. Month 18 and 24 will have a visit window of +/- 2 weeks. Assessments conducted outside these windows will be discussed with the local study team and the decision whether or not to utilize the data in analyses will be documented accordingly.
 2. Converted cases will be followed up as per the schedule of assessments. This will also be the case for participants who commence antipsychotic medication after study enrolment.
 3. Neurocognition tasks: Reading task in English speaking sites will be the WRAT5 Reading subtest; in non-English speaking countries the local version of the NART will be used. Apart from Premorbid and Current IQ, all other cognitive domains will be measured using the Web version of the Penn Computerised Neurocognitive Battery (PennCNB).
 4. The TBI will only be completed for participants where clinically indicated (i.e., participants who have had a traumatic brain injury, as reported by the participant or family or as determined from the participant's medical history).
 5. If conversion to psychosis is suspected based on the monthly BPRS assessment, then the PSYCHS and SCID will be conducted to check conversion status.
 6. Study participants will be contacted in between the formal assessments for the purposes of engagement and safety follow-up (see 8.12).

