8.3. Clinical Assessments

Informed by the recent advances in the field (see section 5.2), the study aims to collect multimodal data (clinical, biological, genetic, neurocognitive, neurophysiological, neuroimaging), baseline and repeat assessments over time ('macro' level monthly assessments) and 'micro-level' momentary (day-to-day) data collected through digital platforms (EMA and passive sensing). The 'macro' level repeat assessments are critical for both dynamic prediction of outcomes and also accurate characterization of clinical trajectories over time.

The battery of assessments are listed in 8.1 and described below. The selection of measures is informed by the Neurobiology in Youth Mental Health Partnership¹⁰¹, a national effort led by Orygen to standardize research assessments in order to create large datasets, guided by principles of feasibility, participant and clinical service burden, transdiagnostic relevance and translatability into clinical practice.

The following measures will be administered by RAs as part of an integrated clinical interview:

The **Positive Symptoms and Diagnostic Criteria for the CAARMS Harmonized with the SIPS (PSYCHS)** is a semi-structured interview which assesses symptoms associated with the prodromal phase of psychosis, and which is used to define the CHR criteria and onset of first-episode psychosis (FEP). The attenuated psychotic symptoms (positive symptoms) section of the PSYCHS will be assessed at all major assessment timepoints. This will be a rating of the worst period of each symptom either (1) over the last year (at Screener) or (2) since the participant's last research assessment.

The **Structured Clinical Interview for DSM-5 (SCID-5)** is a semi structured interview guide for determining DSM-5 diagnoses. The SCID-5-Research Version (RV)⁹⁷ will be used to assess DSM diagnostic criteria for Mood and Substance Use disorders and the SCID-5 Personality Disorders (PD)¹⁰² will be used to assess Schizotypal Personality disorder. If the participant converts to psychotic disorder, as determined using the PSYCHS, then the Psychotic Disorder section of the SCID-5-RV will be administered to determine type of DSM psychotic disorder. The language and diagnostic coverage

make the SCID-5 most appropriate for use with adults (age 18 and over); with slight modification to the wording of questions it may be used with adolescents.

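### Note 1 to the visit schedule lets out-of-window assessments, months 18 and 24 included, be kept or set aside after the result is known, with no criterion and no masking to outcome

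*Protocol*

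**What the plan says.** Section 8.1, Note 1, gives the windows. Up to month 12: "The study team will endeavour to schedule all other visits up to month 12 within +/- 1 week of their due date". After that: "Month 18 and 24 will have a visit window of +/- 2 weeks". For anything outside them the protocol says only that the assessments "will be discussed with the local study team and the decision whether or not to utilize the data in analyses" will be documented. The note makes no exception for the PSYCHS or for the month 24 visit.

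The month 24 visit closes the primary outcome. Section 5.5.1: "The primary outcome of interest is conversion to psychotic disorder by 24 month follow up". Section 7.2 fixes the type of analysis: "Conversion to psychosis is a time-to-event outcome and therefore a survival model such as Cox regression is appropriate".

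On who holds the result, section 8.3 lists the PSYCHS under the statement "The following measures will be administered by RAs as part of an integrated clinical interview", and section 7.3 places those staff at the sites: "Research Assistants (RAs) within their respective clinical service will recruit help-seeking clients". After screening, the PSYCHS rates the worst period of each symptom "since the participant's last research assessment".

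Nothing elsewhere replaces Note 1. Section 13.3.1 lists early or late visits only as examples of deviations, and section 14 has no window rule.

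**The concern.** An assessment can be out of window only once it has been done. By then the local team, whose Research Assistants carried out the interview, knows whether the participant met the conversion threshold. A decision to use or ignore the data, taken in discussion with that team and without a criterion, can depend on the result. Documenting the decision makes it visible but does not stop the dependence.

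This is not a detail left open for an analysis plan. The protocol states a rule, and the rule is discretionary and applied after the result.

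There are no randomised arms, so no treatment comparison is at risk. What could be affected is the conversion rate, the calibration of the prediction models and the associations between predictors and outcome. Section 14 plans to hold back whole sites and test calibration intercept and slope in them. Practice that differed between sites would feed into that test, although nothing in the protocol shows that it would differ.

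**Working it through.** **The plan's own figure.** Section 7.2 assumes 15% conversion over 2 years and gives 300 events for the combined sample of 937 + 1,040 = 1,977. Check: 0.15 × 1,977 = 296.6, which agrees after rounding. For PRESCIENT alone, 0.15 × 937 = 140.6 converters and 796.4 non-converters. The illustration below uses PRESCIENT only, since ProNET's handling of late visits is not in this document.

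**Where the exposure lies.** In Table 2 the BPRS is monthly to month 12, then at months 18 and 24. The PSYCHS is scheduled at baseline, months 1, 2, 3, 6, 12, 18 and 24. Note 5 triggers a conversion check from the monthly BPRS. In the second year, scheduled detection therefore rests largely on the month 18 and 24 visits, both subject to Note 1.

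**Size at month 24.** Assumptions, none of them in the protocol: conversions spread evenly over 24 months; 20% of month 24 visits out of window, equally for converters and non-converters; a participant whose late visit is not used is censored at month 18.

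- Risk to month 18: 0.15 × 18/24 = 0.1125, so the survival proportion is 0.8875.
- At risk after month 18: 937 × 0.8875 = 831.6.
- Events after month 18: 140.6 × 6/24 = 35.1.
- All data used: 1 − 0.8875 × (1 − 35.1/831.6) = 15.0%.

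*Half of the late non-converters dropped.* Late non-converters: 0.20 × 796.4 = 159.3; half is 79.6. At risk: 831.6 − 79.6 = 752.0 (751.9 before rounding the inputs). Estimate: 1 − 0.8875 × (1 − 35.1/752.0) = 15.4%.

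*Half of the late converters dropped.* Late converters after month 18: 0.20 × 35.1 = 7.0; half is 3.5. Events: 31.6. At risk: 828.1. Estimate: 1 − 0.8875 × (1 − 31.6/828.1) = 14.6%.

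*Half of both dropped.* Events 31.6, at risk 748.4. Estimate: 1 − 0.8875 × (1 − 31.6/748.4) = 15.0%. Loss that ignores the outcome leaves the rate where it was; only outcome-dependent loss moves it.

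The same formulas over a range of late shares:

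| Month 24 visits late | Half of late non-converters dropped | Half of late converters dropped |
|---|---|---|
| 10% | 15.2% | 14.8% |
| 20% | 15.4% | 14.6% |
| 30% | 15.6% | 14.5% |

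Selection at month 18 is not included. Onsets concentrated early in follow-up would shrink these shifts.

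**Does a late interview still inform the primary outcome?** Yes, with one condition. Because the PSYCHS looks back to the previous research assessment, an interview at 26 months after a month 18 visit covers months 18 to 26. It can reveal an onset before month 24, but also one after it. Assigning the event needs an onset date. Section 13.2 mentions only that the DPACC will access assessment dates.

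**The case against.** The strongest reply has four parts.

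*The decider is not named.* The note says the matter is discussed with the local team, not that this team decides. The synopsis has the DPACC leading the analysis, and section 14 leaves analytic detail to consultation with the DPACC and the NIMH Steering Committee. This stands: a reader might infer that sites decide alone, and the text does not say so. It does not remove the point, because whoever decides does so after hearing from people who know the result, with no criterion to bind them.

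*Conversions are not simply lost.* The Conversion column of Table 2 and the Note 5 checks have no stated window. Medical records are a back-up for those who cannot be re-interviewed (section 8.13). Coded data still go to the NIMH archive, so an exclusion could be reversed. This also stands, and it narrows the exposure. One might take every out-of-window month 24 visit as a discretionary primary outcome, which at 10–30% late would be 94–281 of 937 participants. That overcounts, since a conversion established by month 18 does not depend on the month 24 visit.

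*The effect is small in a survival analysis.* A simple proportion would give 140.6/(937 − 79.6) = 16.4%, but that removes people from a binary denominator. The planned time-to-event analysis keeps their follow-up to month 18, and the shift falls from 1.4 to about 0.4 percentage points. Accepted.

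*Timing limits have a purpose for some measures.* The SOFAS, persistent negative symptoms and persistent non-psychotic disorders are defined at time points, so accepting visits at any time would blur them. Accepted; the fix treats them separately.

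A reader might also suppose that late attenders are the least well or least engaged. The protocol says nothing on this, and the point does not need it.

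**Conclusion.** The point holds as a defect in a stated rule. Note 1 allows primary-outcome data to be included or set aside with the result known, without a criterion or masking, and no other section overrides it. It shows that selection can occur, not that it will. The local team's knowledge of the result is an inference, but a firm one: its Research Assistants do the ratings and no masking is described.

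The size cannot be determined from the protocol. Under the assumptions shown, month 24 selection in either direction moves the 24-month conversion estimate by roughly 0.2 to 0.6 percentage points from 15.0%. That is modest, and it does not support a claim that the primary outcome is seriously compromised. The change is worth making because the risk is avoidable, touches the primary outcome and costs little to remove.

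**What to change.** Replace the last sentence of Note 1 with a rule that does not depend on the result:

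- **Conversion.** Use every PSYCHS and SCID assessment whatever its timing, analysed in the time-to-event model at its actual date. Record the onset date of each conversion and count onsets by month 24 as events.
- **Point-in-time outcomes and month 2 biomarkers.** For the SOFAS, persistent negative symptoms, persistent non-psychotic disorders and the month 2 repeat biomarkers, prespecify one outer limit. Have it applied centrally, for example by the DPACC, without access to outcome status.
- **Local team.** It supplies only the reason for the deviation.

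The cost is a wording change and, if it is not already captured, one added data item: the conversion onset date. No new visits are needed. The small downside is a longer recall period at late interviews, which makes the onset date somewhat less certain.

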8.2. Demographics, Medical and Psychiatric History

Demographic information (age, sex, gender, race, ethnicity, socioeconomic status, employment, educational attainment and age and education of biological parents) and medical and psychiatric history will be collected. Prior treatment (pharmacological and psychosocial treatment and health service utilisation) will also be captured, based on information collected from the participant and, as required, medical files, family and/or pharmacist.

8.3. Clinical Assessments

Informed by the recent advances in the field (see section 5.2), the study aims to collect multimodal data (clinical, biological, genetic, neurocognitive, neurophysiological, neuroimaging), baseline and repeat assessments over time ('macro' level monthly assessments) and 'micro-level' momentary (day-to-day) data collected through digital platforms (EMA and passive sensing). The 'macro' level repeat assessments are critical for both dynamic prediction of outcomes and also accurate characterization of clinical trajectories over time.

The battery of assessments are listed in 8.1 and described below. The selection of measures is informed by the Neurobiology in Youth Mental Health Partnership¹⁰¹, a national effort led by Orygen to standardize research assessments in order to create large datasets, guided by principles of feasibility, participant and clinical service burden, transdiagnostic relevance and translatability into clinical practice.

The following measures will be administered by RAs as part of an integrated clinical interview:

The **Positive Symptoms and Diagnostic Criteria for the CAARMS Harmonized with the SIPS (PSYCHS)** is a semi-structured interview which assesses symptoms associated with the prodromal phase of psychosis, and which is used to define the CHR criteria and onset of first-episode psychosis (FEP). The attenuated psychotic symptoms (positive symptoms) section of the PSYCHS will be assessed at all major assessment timepoints. This will be a rating of the worst period of each symptom either (1) over the last year (at Screener) or (2) since the participant's last research assessment.

The **Structured Clinical Interview for DSM-5 (SCID-5)** is a semi structured interview guide for determining DSM-5 diagnoses. The SCID-5-Research Version (RV)⁹⁷ will be used to assess DSM diagnostic criteria for Mood and Substance Use disorders and the SCID-5 Personality Disorders (PD)¹⁰² will be used to assess Schizotypal Personality disorder. If the participant converts to psychotic disorder, as determined using the PSYCHS, then the Psychotic Disorder section of the SCID-5-RV will be administered to determine type of DSM psychotic disorder. The language and diagnostic coverage

make the SCID-5 most appropriate for use with adults (age 18 and over); with slight modification to the wording of questions it may be used with adolescents.

Family Interview for Genetic Studies (FIGS)¹⁰³: The FIGS, developed by NIMH, is an instrument that gathers diagnostic information on families in genetic and family studies on mental disorders, such as schizophrenia and bipolar disorders. It offers diagnostic information on each family member of the study participant. The FIGS has been found to be valid and reliable and has been used extensively in previous research. An abbreviated version will be used in the current study, limiting assessment of family history of mental disorder to psychotic, mood and substance use disorders.

The **Social and Occupational Functioning Assessment Scale (SOFAS)**⁹⁸ is a numeric scale (1 through 100) used to rate social and occupational functioning. The SOFAS focuses exclusively on the individual's level of social and occupational functioning, not symptom severity.

The **Global Functioning: Social and Role scales (GF:S and GF:R)**¹⁰⁴ will also be used to rate social and role functioning.

Premorbid Adjustment Scale (PAS): The PAS will be used to assess premorbid functioning across developmental periods and across a number of domains. Each domain is rated on a 0 to 6 point scale, with 0 indicating normal adjustment and 6 indicating severe impairment. The “premorbid” period for PAS purposes is the period ending six months prior to the participant first meeting CHR criteria.

The **Brief Psychiatric Rating Scale (BPRS)**⁹⁴ is a rating scale in which 24 items relating to different types of psychopathology are rated on a continuum of not present to extremely severe. This measure will provide an overall measure of general psychopathology.

The **Negative Symptom Inventory-Psychosis Risk (NSI-PR)**¹⁰⁵. The NSI-PR was designed specifically for measuring negative psychotic symptoms in the CHR population, taking into account aspects of behaviour and socialization that are common to this age range.

The **Overall Anxiety Severity and Impairment Scale (OASIS)**⁹⁵ is a valid and reliable measure of anxiety severity and related impairment. It is a brief (five-item) continuous measure, which can be used across anxiety disorders, with multiple anxiety disorders, and with subthreshold anxiety symptoms. The total OASIS score is calculated by adding together the scores for the five questions. A score of 8 or above suggests clinically significant anxiety.

The **Patient Reported Outcomes Measurement Information System-Sleep Disturbance (PROMIS-SD)**¹⁰⁶ is a brief (8 item) measure of self-reported perceptions of sleep quality, depth, and restoration within the past seven days. This includes perceived difficulties falling asleep and staying asleep, as well as sleep satisfaction.

The **Calgary Depression Scale for Schizophrenia (CDSS)** is a nine item structured interview scale designed specifically to assess depression independently of symptoms of psychosis in schizophrenia¹⁰⁷. It has been validated in CHR samples¹⁰⁸.

The **Alcohol, Smoking and Substance Involvement Screening Test (ASSIST)**⁹⁶, will be used to measure substance use. This measure is widely used and endorsed for the assessment of drug and alcohol use by the World Health Organisation.

The **Columbia Suicide Severity Rating Scale (CSSRS)**¹⁰⁹ assesses suicide risk through a series of simple, plain-language questions. The answers identify whether someone is at risk for suicide, assess the severity and immediacy of that risk, and gauge the level of support that the person needs. The evidence-supported C-SSRS is recommended by the Food and Drug Administration and often referred to as the gold standard for suicide risk assessment. The C-SSRS has been validated in adolescent and adults.

8.4. Self-Report Measures

The following measures will be rated by participants themselves on a tablet:

The **Patient Global Impression of Severity (PGI-S)** is a single item self-report measure assessing a patient's impression of severity of their symptoms over the last 7 days.

Perceived Stress Scale (PSS)¹¹¹: The PSS is the most widely used psychological instrument for measuring the perception of stress. It is a measure of the degree to which situations in one's life are appraised as stressful. Items were designed to tap how unpredictable, uncontrollable, and overloaded respondents find their lives.

Perceived Discrimination Scale (PDS): Perceived discrimination will be assessed using an adapted self-report measure from Jannsen et al (2003)¹¹². Participants answer 'yes' or 'no' to whether they had experienced discrimination in their lifetime because of their skin colour; ethnicity; gender; age; appearance; disability; sexual orientation; religion; or other reason. Total perceived discrimination is calculated as the total number of "types of discrimination" that are endorsed.

Pubertal Development Scale (PDS)¹¹³: This is a self-assessment instrument composed of five questions pertaining to growth spurt, body hair, and changes in skin for both

sexes, rated on 5-point scales: “not yet started” (scored as one point), “barely started” (two points), “definitely started” (three points), “seems complete” (four points), “I don’t know” (treated as missing values). On a similar scale, males also rate their development regarding changes in voice and facial hair growth, while females rate breast growth. Females also state whether they have begun to menstruate.

Psychosis Polyrisk Score (PPS)⁹⁹: This scale was developed based on meta-analyses of environmental risk factors for psychosis. It generates a single score indexing exposure to a range of environmental risk factors associated with psychosis. This single score can be included as a variable in the development of prediction models.

